1.3. Aims

Aim 1. Develop an effective SCT education program for parents of infants with SCT identified by NBS.

- 1a. Determine the feasibility of implementing a SCT education program (SCTaware) that is appropriate for all parents, including those with low baseline knowledge and low health literacy. (Phase I)
- 1b. Determine if significantly more parents who receive SCTaware education have high SCT knowledge 6 months after receiving the education compared to baseline.

Hypotheses: SCTaware will require limited additional resources to implement compared to Ohio's current program and it will result in significantly more parents to have high SCT knowledge.

Approach: A comprehensive team will develop SCTaware education through iterative review and revision of the current in-person program. The time required to train the educator and to administer SCTaware to parents will be recorded. SCTaware will be feasible if educator training can be completed during administrative time and if SCTaware can be provided to parents within Ohio's existing appointment schedule (Phase I). The SCT Knowledge Assessment will measure parents' knowledge before, after, and 6 months post-SCTaware (Phase II).

Aim 2. Determine the barriers that prevent parents of infants with SCT from getting SCT testing.

- 2a. Determine the percentage of parents who obtain on-site SCT testing at time of SCTaware education. (Phase II)
- 2b. Determine the range of decisional conflict that parents may experience regarding SCT testing before and after receiving SCTaware education. (Phase II)

Hypotheses: Making on-site testing available will result in $\geq 50\%$ of parents who are educated to obtain testing. Parents will have decisional conflict about whether to obtain testing that will be reduced with SCTaware education.

Approach: Parents will self-report their SCT status before receiving education. The number of parents that obtain on-site testing will be recorded. We will use the Decisional Conflict Scale to measure parents' uncertainty about obtaining SCT testing before and after education. Parents who do not obtain testing will be asked to report their other testing barriers (e.g., cost, needle phobia, other).

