Pilot Testing SCTaware Education Two new parents will be recruited to pilot test the SCTaware education, to have their SCTaware session video-taped and to complete the associated surveys, but additional parents will be recruited, if needed, so that at least one parent with low health literacy and baseline SCT knowledge pilot test the new program. The Team will the revise the SCTaware program again after reviewing their videos and surveys and pilot test the revised SCTaware program on two additional parents (at least one with low health literacy and baseline SCT knowledge). This process will continue iteratively until the Team agrees that the SCTaware program is finalized. The time required to deliver the SCTaware education during pilot testing will

be recorded. If it is not feasible to deliver SCTaware (i.e. SCTaware education cannot be delivered within the context of the current in-person SCT program), the current in-person SCT education will be tested in Phase II.

Parent stakeholders The NCH hemoglobinopathy team will help the Research Team identify the parent stakeholder of a child with SCT who has previously received the standard SCT education and the parent of a child with SCD who is currently followed by the NCH Hemoglobinopathy Team. These stakeholders will be compensated \$1000 each for their time to review the sessions and to provide their feedback, insights, and lived-experience that will inform the SCTAware education.

Phase II:

Study Design Phase II will be a six-month prospective study.

Recruitment Using the same recruitment strategy as in Phase I, we will recruit 128 parents.

Study Procedures Prior to receiving SCTaware, participants will self-report their SCT status and complete the demographic survey, SCTKA, State Trait Anxiety Index for Adults (STAID), and Decisional Conflict Scales (DCS).

Surveys	Before	After	Follow Up #1	Follow Up #2
	Day 1	Day 1	1 mo	≥6 mo
Demographics	x			
Self-reported SCT status	x		x	x
NVS	x			
SCTKA	x	x	x	x
DCS	x	x	x	
STNA		x		
STAID	x	x		
EES		x	x	x
ebook Survey			x	x

Table 2. Phase II Study Measures

SCTaware sessions will be timed. Participants will complete the DCS, EES, STNA, SCTKA, STAID immediately after their session and a research coordinator will contact parents by telephone one month and ≥6 months after their session to complete additional surveys (Table 2).

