Self-Reported SCT Status and Obtaining SCT testing Parents will self-report their SCT status multiple times during the study to determine if self-reported SCT status is reliable and accurate and impacts their decision to obtain testing. The percentage of parents who obtain on-site testing will be recorded to determine if on-site testing increases SCT status awareness and if tested parents can accurately recall their status ≥6 months after they were tested.

STAID (short form) Qualitative studies suggest that SCT education has the potential to reduce parental anxiety.⁶ The STAID short form is a 20-item sensitive and reliable measure of state anxiety and will be used to quantify parents' anxiety before and after receiving SCTaware education (Table 3).^{14,15}

DCS Participants will complete the 16-item validated tool to determine if decisional uncertainty is a SCT testing barrier for parents and if SCTaware increases parents' perception that they made an informed decision about whether to obtain testing. DCS has predictive validity over a range of decisions, and in studies of decision-supporting interventions, effect sizes ranged from 0.4-1.2.¹³⁻¹⁵

ebook Survey While most parents will have an electronic device, the non-interactive ebook content will be printed. Parents will be asked to report the type of device(s) they have since readability may differ by device, and to provide feedback on the content and format. They will also be asked to report how often they accessed the ebook since their in-person education to support their learning or to share information about SCT with their families and communities.

Time to Deliver SCTaware Education and Notifications Although health literacy-based methods can marginally increase the time to deliver information, in return, more learners may comprehend the information presented.¹⁶ We will compare the time to provide SCTaware education (Phase II) to Ohio's current in-person SCT education (Phase I). We anticipate that familiarity with SCTaware will reduce delivery time. The time to deliver parents' test results will also be recorded to determine if this testing can be included within the SCTaware program.

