7. Survey Completion- A research coordinator will read all survey items to participants and record their responses electronically. This format will be used because participants are only required to have functional verbal English and the NVS was validated using an interview format. This will also ensure that the method of survey completion is consistent in Phase II because the follow up surveys at 1 and 6 months will be over the telephone.

8. Study Compensation

Phase I: Participants will receive \$25 for completing Phase I.

Phase II: Participants will receive \$25, \$5, and \$10 for completing the initial, 1-month, and 6-month surveys, respectively.

9. Safety

a. Privacy

Participants' data will be de-identified to minimize the risk that participants' survey responses will be intercepted by a third party. The assessments will be completed electronically and stored in Redcap.

b. Data Storage

The survey results will be stored on a research drive that is maintained behind NCH secure firewall. The research data will be retained for 7 years after publication of the data, in accordance with standard research methods. After this time all collected data will be destroyed.

10. Data Management and Statistical Analysis

a. Data Monitoring

Study data will be collected, downloaded, and stored on RedCap. This database will only contain de-identified patient adherence data and will be linked by study ID number.

b. Statistical Methods and Analysis

Phase I: SCTaware will be deemed feasible if educator training and the time to deliver SCTaware can be delivered within the context of the current SCT program at NCH.

Phase II: During our preliminary study, ~40% of parents had high SCT knowledge prior to receiving education and 90% percent of parents achieved high SCT knowledge immediately after they received the current standard education program,⁵ however, it was unclear if this knowledge was sustained at 6 months because few parents completed the 6-month SCTKA. To determine if significantly more parents who receive SCTaware education have high SCT knowledge 6 months after receiving the education compared to baseline (Aim 1b, the primary aim for Phase II of the study), we will enroll 128 (n=98 evaluable) parents on Phase II of the study. This sample size was calculated using a two-sided, McNemar's test and has 80% power, with a 5% alpha, and assumes 30% attrition (Aim 1b).

Study Design	Knowledge Level at 6-month after SCTaware		

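### The delivery-time half of Aim 1a feasibility rests on a handful of Phase I pilot sessions, and the timed Phase II sessions are never checked against the appointment slot that defines it

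*Combined protocol and SAP*

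**What the plan says.** Aim 1a (section 1.3) is assigned to Phase I and has two operational criteria. One concerns training: "SCTaware will be feasible if educator training can be completed during administrative time". The other concerns delivery: "if SCTaware can be provided to parents within Ohio's existing appointment schedule (Phase I"). Section 10.b restates both, under Phase I only, as feasibility being "deemed feasible if educator training and the time to deliver SCTaware can be delivered within the context of the current SCT program". No appointment length in minutes and no required share of sessions is given.

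The evidence on delivery comes from the pilot described in section 5.f (Pilot Testing SCTaware Education). "Two new parents will be recruited to pilot test the SCTaware education"; the team then revises the programme and will "pilot test the revised SCTaware program on two additional parents". Each pair must include at least one parent with low health literacy and low baseline knowledge. The stopping rule is agreement: "This process will continue iteratively until the Team agrees that the SCTaware program is finalized". Pilot delivery times are recorded. If delivery does not fit the current programme, the current education goes into Phase II instead.

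Section 5.f also has the Phase II SCTaware sessions timed. Section 6 (Time to Deliver SCTaware Education and Notifications) gives the only stated use of those times: "We will compare the time to provide SCTaware education (Phase II") with the current in-person education timed in Phase I. Under Program Evaluation in section 5.f, that comparator is five parents' sessions, with more only if too few parents have low literacy or low knowledge.

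**The concern.** The question is whether sessions fit the slot. The plan answers it from very few early sessions and then collects a far larger set of session times that is not put to the same question.

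The planned Phase I versus Phase II comparison cannot stand in for that check. SCTaware could take longer than the current education and still fit the appointment. It could also differ little on average while a material share of sessions overrun. Section 6 itself expects health-literacy methods to add some time and familiarity to take some away. Both effects would play out over Phase II and could hardly be seen in two to four pilot sessions.

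At stake is the reliability of a named aim. Aim 1a could be reported as met with little information behind it. If Phase II sessions then ran over, nothing in the plan says the feasibility statement would be revisited. The primary Phase II aim (1b) is not affected.

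**Working it through.** The plan gives no sample size, threshold or precision for feasibility, so there is no figure of its own to reproduce.

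**Inputs**
- Current-programme sessions timed in Phase I: 5, with possible top-up (section 5.f).
- Pilot sessions: 2, a revision, then 2 more, so at least 4 in all and as few as 2 of the last piloted version (section 5.f). The minimum path uses 5 + 2 + 2 = 9 parents, which is consistent with the approximately 5-10 in section 5.d.
- Phase II: 128 parents (sections 5.d and 10.b). This is 128 sessions if each parent attends alone. It is fewer if two parents of a child attend together, which section 2.5 makes possible by allowing both to enrol. I use 90 sessions as an illustrative lower count.
- Assumptions: true overrun rates of 20%, 30% and 50% as a range, because the documents give neither an overrun rate nor a slot length.

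**1. What the pilot can exclude.** If all n sessions fit, the one-sided 95% upper limit for the overrun rate is 1 − 0.05^(1/n).
- n = 4: 1 − 0.05^(1/4) = 0.527, or 53%.
- n = 2: 1 − 0.05^(1/2) = 0.776, or 78%.

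**2. Chance that every pilot session fits when the true overrun rate is q:** (1 − q)^n.

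| True overrun rate q | Both of 2 fit | All 4 fit |
|---|---|---|
| 20% | 64% | 41% |
| 30% | 49% | 24% |
| 50% | 25% | 6% |

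**3. The planned use of Phase II times.** For a difference in mean session length, in units of the session-length SD (assumed equal in both groups), the 95% half-width is t × √(1/n₁ + 1/n₂).
- 5 vs 128: 1.978 × √(1/5 + 1/128) = 1.978 × 0.456 = 0.90 SD.
- 5 vs 90: 1.986 × √(1/5 + 1/90) = 1.986 × 0.459 = 0.91 SD.

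The five older sessions set the precision, so the size of Phase II makes almost no difference.

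**4. The same Phase II times judged against the slot.** Exact (Clopper-Pearson) 95% CIs at about 10% overruns:
- 13 of 128 = 10.2%: 5.5% to 16.7%.
- 9 of 90 = 10.0%: 4.7% to 18.1%.

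**5. Subgroups.** Section 10.b puts high baseline knowledge at about 40%, so about 60% are low. Section 5.f reports more than 50% with low literacy and baseline knowledge in the preliminary study. A combined group (low on either) would be at least about 60% of parents. If the two were independent, it would be about 1 − 0.4 × 0.5 = 80%. A combined group would therefore be most of the sample, so the two should be reported separately.

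**The case against.** The strongest reply is that this is a deliberate design. Feasibility is a Phase I gate deciding which programme enters Phase II, and a small pilot is an ordinary basis for a go/no-go. That stands, and the gate should be kept.

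Other points also stand in whole or part:
- At least four pilot sessions are timed, and the earlier version says something about duration. Counting only the last pair gives the less favourable figure, so both are shown.
- Times are recorded as durations. Sessions finishing far inside the slot would be more reassuring than a bare count of those that fit. Without the slot length, neither this nor the real overrun risk can be assessed from the documents.
- Training time is half of the criterion, and Phase II session times cannot inform it.
- The Phase I versus Phase II comparison is not pointless. It addresses the hypothesis in section 1.3 that SCTaware needs few extra resources relative to Ohio's current programme, and longer sessions would show there, if imprecisely.

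A reader might also infer that Aim 1a promises schedule fit for every literacy level, because it speaks of a programme "appropriate for all parents, including those with low baseline knowledge and low health literacy". That phrase describes the programme. Suitability of the materials is handled separately through SAM, CDCCI and PEMAT scores. Nor do the documents say that teach-back lengthens sessions most for low-literacy parents; section 6 expects only a marginal increase in general.

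None of this answers the remaining point: the larger set of timings is never compared with the criterion that defines delivery feasibility.

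**Conclusion.** The concern holds for the delivery-time half of Aim 1a. A clean pilot would leave overrun rates of up to 53% (four of four) or 78% (two of two) unexcluded. The planned Phase II time comparison is precise only to about 0.9 SD and answers a different question. The same Phase II timings, set against the slot, would give an interval of about 11 to 13 percentage points at 10% overruns.

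These limits treat each session as an independent fit-or-overrun outcome with a common rate. The plan does not state its criterion in that form. The overrun rates in the working are assumptions, and the Phase II figures depend on how many parents attend together.

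It would go too far to infer that SCTaware is likely to overrun, that the Phase I gate is invalid, or that the whole of Aim 1a should move to Phase II. The documents give no slot length from which to judge overruns, a small gate is a legitimate choice, and the training criterion belongs in Phase I.

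**What to change.** - Keep the Phase I pilot as the go/no-go for Phase II, and keep the educator-training criterion in Phase I.
- State the scheduled appointment length in the protocol. Before Phase II starts, have the team set the share of sessions that must finish within it.
- Confirm or revise the delivery-time part of the Aim 1a conclusion from the percentage of timed Phase II SCTaware sessions that finish within that length, counted per session, with an exact 95% CI, judged against the pre-set share.
- Report the same percentage separately for sessions that include a parent with NVS <4 and for sessions that include a parent with baseline SCTKA <75%, not as one combined group.
- Keep the Phase I versus Phase II time comparison and label it descriptive.

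Session times, NVS and baseline SCTKA are already collected, so the cost is protocol wording and one extra table. The downside is that the feasibility statement is finalised later and may be less favourable.

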	Proportion with High Knowledge	Proportion with Low Knowledge	
Knowledge Level pre-SCTaware Education	Proportion with High Knowledge	30%	15%
	Proportion with Low Knowledge	35%	20%

Similar to our preliminary results, this example assumes that 45% of participants will have high SCT knowledge before receiving SCTaware and 65% will have high SCT knowledge 6 months after receiving SCTaware education. Therefore, a sample of 98 evaluable participants will have 80% power to detect an odds ratio of 2.33 when the proportion of discordant pre and post-SCTaware pairs is 0.5.

11. Quality Assurance

a. Training of research Staff

Prior to enrollment, the research team will meet to review all protocol procedures, including screening, enrollment, and survey administration. The PI will insure that all research staff who consent, enroll, and complete study follow up assessments are adequately trained. The research team will meet at least monthly during active enrollment and to discuss any potential problems and then at least bi-monthly while participants are still actively participating in the study.

12. Dissemination of Results and Publication

a. Planned Journal for Submission

Phase I: J Genet Counseling

Phase II: Pediatrics

b. Authorship

[name], [name], [name], [name], [name], [name]

13. Timeline

Dates	Phase
April 2019-October 2019	Phase I
October 2019-April 2021	Phase II

14. Anticipated Problems and Solutions

1. Meeting recruitment goals is a challenge of all studies, however, this study will use the same strategy that successfully enrolled 91% of eligible parents in <12 months. To further encourage participation, this study will also include participation incentives and we have also expanded the eligibility criteria to include parents with functional verbal English (do not request interpreter services).

2. Recruitment bias is possible, since only parents who present for in-person education will be included. Once SCTaware is developed, however, adapting the program for electronic delivery may increase the number of parents who can receive this strategy.

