3. The primary aim of Phase II of the study is to determine if more parents achieve high SCT knowledge at 6-months. Since these parents do not necessarily have ongoing communication that is standard with the SCT educator and our prior experience suggests that study attrition may be higher than in other studies, we will enroll more parents in anticipation of higher attrition (30%). Also, to reduce attrition during Phase II, we will collect multiple contact methods for participants at enrollment (email, address, telephone number) and confirm these are still accurate at the one-month follow up. Small monetary compensation will also be provided throughout to encourage completion of all study activities.

4. The Ohio Department of Health only has resources to provide one-time SCT education for each parent and is aware and has endorsed this project (provided a letter of support with the R03 grant application). If participants request that they want an additional session, the Team will provide a group SCT session for participants after they complete their 6-month surveys.

5. The research team will inform parents of the potential that SCT testing could identify non-paternity. To ensure privacy, the research team will only disclose SCT test results to the tested parent.

References

1. Centers for Disease Control and Prevention, Data and Statistics: Sickle Cell Disease <https://www.cdc.gov/ncbddd/sicklecell/data.html>. Accessed July 27, 2017.

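### 128 enrolled parents with 30% attrition leave about 89 or 90 evaluable, not 98, so the stated 80% power for the primary Phase II aim is not delivered

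*Combined protocol and SAP*

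**What the plan says.** Section 10b (Statistical Methods and Analysis, Phase II) sets the sample size for Aim 1b, which it names as the primary aim of Phase II: "we will enroll 128 (n=98 evaluable) parents on Phase II of the study". The size was "calculated using a two-sided, McNemar's test", and the same sentence says it "has 80% power, with a 5% alpha, and assumes 30% attrition".

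The text around the planning table assumes that "45% of participants will have high SCT knowledge before receiving SCTaware and 65% will have high SCT knowledge 6 months after" the education. The discordant cells are 35% (low to high) and 15% (high to low). It concludes that "a sample of 98 evaluable participants will have 80% power to detect an odds ratio of 2.33" with half of the pairs discordant.

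The figures recur elsewhere. The enrolment target of 128 is in section 5d (Enrollment) and in the Phase II recruitment text of section 5f. The 30% is repeated in section 14, item 3, as the reason for enrolling more parents than the test needs.

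**The concern.** The plan gives an enrolled number, an attrition rate and an evaluable number, and any two of them fix the third. Applying the stated rate to the stated enrolment does not give the stated evaluable number. No section offers another attrition rate, or a definition of attrition, that would reconcile them.

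The power claim is tied to 98 evaluable parents. If 30% are lost, the primary McNemar comparison runs on fewer pairs than the claim requires. Attrition is also the risk that the plan itself stresses: section 10b reports that few parents in the preliminary study completed the 6-month knowledge assessment, and section 14 expects heavier losses than other studies see. The 30% is therefore a deliberate allowance, and the enrolment target should honour it.

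**Working it through.** **Inputs, all from section 10b:** two-sided McNemar test, alpha 0.05, power 80%; discordant cells 0.35 and 0.15; 98 evaluable; 128 enrolled; 30% attrition (also in section 14, item 3).

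Discordant proportion: pd = 0.35 + 0.15 = 0.50. Difference: d = 0.35 - 0.15 = 0.20, which equals 65% - 45%. Odds ratio: 0.35 / 0.15 = 2.33, as stated.

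**Step 1: reproduce the 98.** By the normal approximation,

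n = (1.96 x sqrt(pd) + 0.8416 x sqrt(pd - d²))² / d² = (1.96 x sqrt(0.50) + 0.8416 x sqrt(0.46))² / 0.04 = 95.7, so 96.

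The stated 98 is within two pairs of this. Power at 98 is 80.9%. The evaluable number is sound.

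**Step 2: the attrition step.**

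- Evaluable if 30% of 128 are lost: 128 x 0.70 = 89.6, so 89 or 90.
- Enrolment needed to keep 98 at 30% loss: 98 / 0.70 = 140.
- Attrition implied by 128 and 98: 30 / 128 = 23.4%.
- Multiplying instead of dividing: 98 x 1.30 = 127.4, rounded up to 128, which is the stated enrolment.

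**Step 3: power at the number actually left.** With the same cells,

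power = Φ((d x sqrt(n) - 1.96 x sqrt(pd)) / sqrt(pd - d²)).

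For n = 89: (0.20 x 9.434 - 1.386) / 0.678 = 0.739, and Φ(0.739) = 77.0%.

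Section 10b does not say which version of the test is meant, so the other versions were enumerated over all possible numbers of discordant pairs:

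| Version | n = 89 | n = 90 | n = 98 |
|---|---|---|---|
| Normal approximation | 77.0% | 77.5% | 80.9% |
| Asymptotic, uncorrected (enumerated) | 77.7% | 78.2% | 81.6% |
| Mid-p (enumerated) | 77.7% | 78.2% | 81.6% |
| Exact (enumerated) | 73.5% | 74.0% | 78.0% |
| Continuity-corrected (enumerated) | 72.6% | 73.1% | 77.5% |

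None reaches 80% at 89 or 90 pairs.

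**Step 4: detectable effect.** With 89 pairs, half of them discordant, the odds ratio detectable with 80% power is about 2.42 (normal approximation), against the stated 2.33.

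**The case against.** The strongest reply is that the effect is small: 8 or 9 pairs and 3 to 4 points of power under the asymptotic test. Type I error, endpoint and test are untouched, and nothing is biased. The planning table is offered as an example, and its cells matter more than 89 against 98. If the discordant split were 40%/15% or 30%/10% (assumed values, not the plan's), power at 89 pairs would be about 90% or 86%. All of that stands as a measure of size. None of it makes the three figures agree, and a more favourable table is not what the plan assumed.

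A second reply is that 80% power is claimed only for 98 evaluable parents, and that claim is correct. Since 96 pairs suffice by the normal approximation, 128 enrolled tolerates 25% attrition (96 / 128 = 0.75), and section 14 lists retention measures that might hold losses there. This is fair as far as it goes: the power is missed only if losses exceed about 25%. But section 14 sets out those measures alongside the 30%, not as grounds for a lower rate. The margin of two pairs does not cover a shortfall of eight or nine.

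Third, the plan does not show how 128 was obtained, so multiplication by 1.30 is an inference. It matches exactly, and the contradiction does not depend on it.

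**Conclusion.** The point holds. The enrolled number, evaluable number and attrition rate for the primary Phase II aim are mutually inconsistent. At the plan's own 30% attrition, 89 or 90 parents are evaluable and power is about 77% by the normal approximation, with a range of about 73% to 78% across versions of the test.

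This rests on the plan's own planning table and on attrition meaning the share of enrolled parents who are lost, which is how section 14 uses it. The fault lies only in the attrition step; the calculation of 98 evaluable is acceptable for the asymptotic test.

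**What to change.** Make the figures in section 10b and section 14, item 3, agree.

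- **Keep 128 (simplest).** State that at 30% attrition about 89 parents will be evaluable, giving about 77% power for an odds ratio of 2.33, or 80% power for about 2.42. This is a wording change; its only cost is a slightly less favourable power statement.
- **Enrol 140** if 80% power at 30% attrition is required. That is 12 more parents, and the 128 in sections 5d and 5f must change too. The population section reports that about 500 infants a year typically have at least one parent attend.
- **Keep 128 and 98 and state a 23% allowance** only if there is evidence for that rate. The documents give none, and section 14 argues for 30%.

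In the same edit, name the version of McNemar's test. The exact test needs 103 pairs for 80% power at the planned table, which at 30% attrition is 103 / 0.70 = 147.1, so 148 enrolled. Enrolling 140 restores 80% for the asymptotic test but not for the exact one.
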